## ***I) Administrative information***

- 1) **Title:** " Effect of Dissolving Xylitol Chewable Tablets versus Xylitol Chewing Gum with Geriatric Bedridden Patients on Salivary pH and Bacterial Count in Both Saliva & Interdental Plaque :  
Randomized Clinical Trial"
- 2) **Trial registration:** Trial will be registered in <https://clinicaltrials.gov/>
- 3) **Protocol version:** This is the first version of the protocol (March 2019).
- 4) **Funding:** No funding from any parties
- 5) **Trial sponsor:** Faculty of Dentistry, Cairo University.
- 6) **Roles and responsibilities:**

**Bacteriological Assessment:**

Department of microbiology, Faculty of medicine, Cairo university.

**Research Ethics Committee (REC)** of Faculty of Dentistry, Cairo University; For reviewing protocol of this clinical trial to protect the rights, safety, dignity and well-being of the people participating in the trial.

**Research Plan Committee:**

Conservative Dentistry Department, Faculty of Dentistry, Cairo University; for ensuring that this protocol is following the department research plan.

## **II. INTRODUCTION**

### **1) Background and Rationale:**

#### **1.1. Research question:**

For the geriatric bedridden patients, will the use of the newly introduced dissolving Xylitol chewable tablets be better in decreasing bacterial count in both saliva and interdental plaque and elevating the salivary pH if compared against xylitol chewing gum?

#### **1.2. Statement of the problem:**

Dental caries remains the most prevalent chronic disease in both children and adults, and is one of the most common important global oral health problems in the world, but it is largely preventable (**Yadav and Prakash, 2016**). Although caries has significantly decreased over the past four decades, disparities remain among some population groups like geriatric patients and the scenario becomes even more accentuated when it comes to bedridden patients, who are dependent and whose functional capacity is shortened. Moreover, they usually face the given reality that they are constrained to their rooms, without having access to the bathroom which strict their ability for tooth brushing and mouth rinsing (**Morandi et al, 2018**).

#### **1.3. Rationale:**

So, these bedridden patients who may not have ready access to water are most need of easy swallowing dosage forms like chewable tablets (**Renu et al,2015**). Using chewable tablets like the newly introduced "Listerine Ready Tabs" that can be swallowed give them the opportunity to clean their mouth without leaving their beds.

#### **1.4. Review of literature:**

During the latter half of the 20th century, the age composition of the population changed dramatically, with more people living to older ages and the older population getting older. This demographic change will have a major impact on the delivery of general and oral health care. (*Abdul razaq, 2014*). Improved quality of life at old age will demand tooth retention. However, Retaining teeth disease free and maintaining preventive care for elderly people, is a multi- faceted challenge. (*Roopa et al, 2011*)

Many elderly persons are hampered in their efforts of performing plaque control procedures by physical disabilities that result in the lack of manual dexterity or impaired range of motion of the wrist, elbow or shoulder (*Abdul razaq 2014*). Moreover, the scenario becomes even more accentuated when it comes to bedridden patients as they are constrained to their rooms, without having access to the bathroom which strict their ability for tooth brushing and mouth rinsing. So, such population must take much more interest from us for their oral care.

Xylitol, which presents in our interventions , is a naturally occurring five-carbon sugar polyol .It is a white crystalline carbohydrate known since a century ago. It has been widely studied during the last 40 years for its effect on dental caries. It is found naturally in fruit, vegetables, and berries and is artificially manufactured from xylan-rich plant materials such as birch and beechwood. (*Nayak et al, 2014*)

Xylitol reduces the levels of mutans streptococci (MS) in plaque and saliva. It also reduces their acid production potential leading to increase in salivary ph. (*Nayak et al, 2014*)

It was found that the xylitol bacteriostatic effect on *S. mutans* is by creating a futile cycle that consumes cellular ATP. In a futile cycle, Xylitol is transported across bacterial cell membrane by a phosphotransferase system, generating xylitol-5-phosphate which can not be metabolized and may subsequently be dephosphorylated and exported at the expense of ribitol-5-phosphate . ( *Chen and Wang, 2010* )

*Ly et al in 2006* determined the reduction in mutans streptococci levels in plaque and unstimulated saliva to increasing frequency of xylitol gum use at a fixed total daily dose of 10.32 g over five weeks. They randomized participants (n = 132) to either active groups (10.32 g xylitol/day) or a placebo control (9.828 g sorbitol and 0.7 g maltitol/day). All groups chewed 12 pieces/day. The control group chewed 4 times/day and active groups chewed xylitol gum at a frequency of 2 times/day, 3 times/day, or 4 times/day. The 12 gum pieces were evenly divided into the frequency assigned to each group. Plaque and unstimulated saliva samples were taken at baseline and five-weeks and were cultured on modified Mitis Salivarius agar for mutans streptococci enumeration. They found no significant differences in mutans streptococci level among the groups at baseline. At five-weeks, mutans streptococci levels in plaque and unstimulated saliva showed a linear reduction with increasing frequency of xylitol chewing gum use at the constant daily dose. Although the difference observed for the group that chewed xylitol 2 times/day was consistent with the linear model, the difference was not significant. They concluded that there was a linear reduction in mutans streptococci levels in plaque and saliva with increasing frequency of xylitol gum use at a constant daily dose. Reduction at a consumption frequency of 2 times per day was small and consistent with the linear-response line but was not statistically significant.

*Milgrom et al in 2006*, determined the dose-response of mutans streptococci in plaque and unstimulated saliva to xylitol gum. They randomized participants (n = 132): controls (G1) (sorbitol/maltitol), or combinations giving xylitol 3.44 g/day (G2), 6.88 g/day (G3), or 10.32 g/day (G4). Groups chewed 3 pellets/4 times/d. Samples were taken at baseline, 5 wks, and 6 mos, and were cultured on modified Mitis Salivarius agar for mutans streptococci and on blood agar for total culturable flora. They found that at 5 wks, mutans streptococci levels in plaque were 10x lower than baseline in G3 and G4 (P = 0.007/0.003). There were no differences in saliva. At 6 mos, mutans streptococci in plaque for G3 and G4 remained 10x lower than baseline (P = 0.007/0.04). Saliva for G3 and G4 was lower than baseline by 8 to 9x (P = 0.011/0.038). They concluded that xylitol at 6.44 g/day and 10.32 g/day reduces mutans streptococci in plaque at 5 wks, and in plaque and unstimulated saliva at 6 mos. A plateau effect is suggested between 6.44 g and 10.32 g xylitol/day.

*Prathibha et al in 2010* compared the effect of Manuka honey, chlorhexidine gluconate (0.2%) mouthwash and xylitol chewing gum on the dental plaque levels. Sixty healthy male dental students aged between 21 and 25 years (mean age 23.4 years) participated in the study. All the subjects received a professional prophylaxis at the start of the study, with the purpose of making the dentition 100% free of plaque and calculus. The subjects were then randomly divided into three groups, i.e. the Manuka honey group, the chlorhexidine gluconate mouthwash group and the xylitol chewing gum group. Rinsing with water or any other fluid after the procedure was not allowed as also any form of mechanical oral hygiene for all the subjects during the experimental period of 72 h. After the experimental period, the plaque was disclosed using disclosing

solution and their scores were recorded at six sites per tooth using the Quigley and Hein plaque index modified by Turesky-Gilmore-Glickman. They found that the mean plaque scores for Groups I, II and III were 1.37, 1.35 and 1.57, respectively. The ANOVA revealed that between group comparison was significant, with an F-value of 5.99 and a probability value of 0.004. The T-test was carried out to evaluate the inter-group significance, which revealed that the plaque inhibition by Manuka honey was similar to that of chlorhexidine mouthwash. So they concluded that both Manuka honey and chlorhexidine mouthwash reduced plaque formation significantly, better than the xylitol chewing gum.

*Kumar, et al in 2013*, evaluated the salivary and dental plaque pH changes after consumption of sugared and sugar-free (xylitol) chewing gums in children. They selected a total of 30 school children for this study and divided them into two equal groups and gave both chewing gums for the experiment. They found that children consuming the sugar-free (xylitol) chewing gum showed a marked increase in the pH of saliva and plaque when compared to their counterpart. All these values had a significant difference of  $P \leq 0.0001$ . So, they concluded that xylitol is a safe natural sweetener which helps to reduce tooth decay. It plays a unique role in preventive strategies for better health.

*Nishihara et al in 2014* evaluated the effects of the lactic acid bacterium *Lactobacillus salivarius* on caries risk factors. They performed their study in 64 healthy volunteers to evaluate the effects of *L. salivarius*-containing tablets on caries risk factors. They divided participants randomly into four groups, and gave them chewable tablets containing *L. salivarius* WB21, *L. salivarius* TI 2711, Ovalgen® DC (antibody against glucosyltransferase from *Streptococcus mutans*), or

xylitol and then levels of mutans streptococci and lactobacilli, amount of salivary flow, salivary pH, and salivary buffering capacity were assessed before and after taking the tablets. They found that the levels of mutans streptococci seemed to decrease in the L. salivarius WB21, TI 2711, and Ovalgen® DC groups compared to the xylitol group, with no significant differences between the groups. Lactobacilli levels significantly increased in the L. salivarius WB21 and TI 2711 groups compared to the other groups. Concerning salivary flow and salivary pH, they found no significant differences between the groups. Also they found that the salivary buffering capacity significantly increased in the L. salivarius TI 2711 group (P = 0.003) and Ovalgen® DC group (P = 0.002) compared to the xylitol group. And finally they found that, the L. salivarius WB21-containing tablets significantly decreased the number of mutans streptococci (P = 0.039).

*Lapiedra et al in 2015*, evaluated the effect of a combination saliva substitute for the management of xerostomia and hyposalivation. They evaluated the difference between the combination agent of xylitol, beatine and olive oil in a chewable capsule versus the control agent of a sorbitol tablet in subjects with hyposalivation and xerostomia. Their study was 3 weeks in duration, with 2 treatment phases of 1 week and a 7 day wash out period in between. At the end of each treatment phase, subjects returned for a follow up evaluation. At this visit they gave the patients subjective sensation questionnaire, as well as they measured their unstimulated whole salivary flow and stimulated whole salivary flow. They found that there was a greater increase in the unstimulated and stimulated whole salivary flow rate, although the results were not statistically significant. The subjective evaluation as measured by the questionnaire showed that both agents reduced the mean score as

compared to the baseline, although only the findings in the active agent was statistically significant ( $p = 0.0015$ ). They concluded that the active agent provided a significant subjective improvement in speech, swallowing, and decreased subjective xerostomia as compared to the control tablet.

*Masoud et al in 2015* evaluated long-term clinical and bacterial effects of using 6 g of xylitol per day for 3 months on patients with full fixed orthodontic appliances. They made a pilot clinical trial that included 41 subjects who were undergoing orthodontic treatment. They divided subjects randomly into three groups. Group A received xylitol chewing gum, group B received xylitol dissolvable chewable tablets, and Group C served as the control group and did not receive xylitol gums or tablets. Clinical examination and the collection of plaque and saliva samples were carried out at baseline and 3, 6, and 12 months. All three groups were given oral hygiene instruction and were put on a 6-month cleaning and topical fluoride schedule. Plaque scores and bacterial counts were used to evaluate the effectiveness of the different approaches at reducing the caries risk. They found that xylitol groups did not experience any more reduction in plaque score, plaque MS counts, or salivary MS counts than the control group nor did they have lower values at any of the time points. They concluded that xylitol does not have a clinical or bacterial benefit in patients with fixed orthodontic appliances. Oral hygiene instructions and 6-month topical fluoride application were effective at reducing plaque scores and bacterial counts in patients with full fixed appliances regardless of whether or not xylitol was used.

*Cock et al in 2016* provided a comprehensive overview of published evidence on the impact of erythritol, a noncaloric polyol bulk sweetener, on oral health. *Methods*. A literature review was conducted

regarding the potential effects of erythritol on dental plaque (biofilm), dental caries, and periodontal therapy. The efficacy of erythritol on oral health was compared with xylitol and sorbitol. They found that Erythritol effectively decreased weight of dental plaque and adherence of common streptococcal oral bacteria to tooth surfaces, inhibited growth and activity of associated bacteria like *S. mutans*, decreased expression of bacterial genes involved in sucrose metabolism, reduced the overall number of dental caries, and served as a suitable matrix for subgingival air-polishing to replace traditional root scaling. They concluded that important differences were reported in the effect of individual polyols on oral health with the evidence demonstrating better efficacy of erythritol compared to sorbitol and xylitol to maintain and improve oral health.

**Rafeek et al in 2019**, conducted a study to see if chewing gum containing xylitol may help prevent caries by reducing levels of mutans streptococci (MS) and lactobacilli in saliva and plaque. In this study, they employed high-throughput sequencing of the 16S rRNA gene to profile microbial communities of saliva and plaque following short-term consumption of xylitol and sorbitol containing chewing gum. Participants (n = 30) underwent a washout period and were randomly assigned to one of two groups. Each group chewed either xylitol or sorbitol gum for three weeks, before undergoing a second four-week washout period after which they switched to the alternate gum for three weeks. Upon analysis of samples collected before and after each intervention, they identified distinct plaque and saliva microbial communities that altered dependent on the order in which gum treatments were given. They found that neither the xylitol nor sorbitol treatments significantly affected the bacterial composition of plaque. Lactobacilli were undetected and the number of Streptococcus mutans sequence reads was very low and unaffected by either xylitol or sorbitol. However, sorbitol affected several other streptococcal species in saliva including increasing the abundance of *S. cristatus*, an oral commensal shown to inhibit bacteria associated with chronic periodontitis.

## **1.5. Choice of comparator:**

In our study , the comparator is xylitol chewing gum as *Nayak et al in 2014* mentioned that the predominant modality for xylitol delivery has been chewing gum, as moreover the antibacterial effect of xylitol , chewing a gum accelerates the processes of rinsing away acid by stimulating salivary flow and uptake of benefacial calcium phosphate molecules to remineralize tooth enamel. ( *Chen and Wang, 2010*)

And another special cause in this study is our population who are geriatric bedridden patients. As chewing a soft gum is a simple, easy, convenient independent procedure that don't need any physical effort or caregiver and also don't need from them to leave their beds or to go to the bathroom like for brushing or rinsing.

## **2) Objectives:**

### **2.1. Aim of the study:**

This study will be conducted to evaluate the effectiveness of using dissolving Xylitol chewable tablets versus xylitol chewing gum with bedridden geriatric patients ,as an alternative to tooth brushing and mouth rinsing, in increasing salivary pH and decreasing bacterial count in both saliva and interdental plaque.

### **2.2. Hypothesis:**

The null hypothesis is that the newly introduced dissolving xylitol chewable tablets have the same effect as xylitol chewing gum on salivary pH and bacterial count in both saliva and interdental plaque when used with geriatric bedridden patients.

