**O (outcome) :**

**O1:** salivary streptococcus mutans count

**O2:** interdental plaque bacterial count

**O3:** salivary pH

Type	Outcome Name	Measuring Device	Measuring Unit
1ry	Salivary S.mutans count	Bacterial Culture	CFU/ml
2ry	Interdental plaque Bacterial count	Bacterial Culture	CFU/ml
3ry	Salivary pH	pH Meter	Moles per litre

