## 3) Sample size calculation:

A power analysis was designed to have adequate power to apply statistical test of the research hypothesis that dissolving xylitol chewing tablets will have the better antibacterial effect than xylitol chewing gum against mutans streptococci after 1 month. According to the results of *Swapnil et al. in 2018* in which the probability of bacterial count reduction to  $10^2$  for xylitol chewing gum (comparator) was (0.15), probability of bacterial count reduction to  $10^3$  was (0.6) and probability of bacterial count reduction to  $10^4$  was (0.25) with effect size  $w=0.578$  ( $n=29$ ). If the estimated probability of dissolving xylitol chewing tablets for bacterial count reduction to  $10^2$  is (0.35), probability of bacterial count reduction to  $10^3$  is (0.5) and probability of bacterial count

reduction to  $10^4$  was (0.15) with effect size  $w=0.43$  ( $n=53$ ). By adopting an alpha ( $\alpha$ ) level of 0.05 (5%), power=80%. The predicted sample size ( $n$ ) was a total of (82). Sample size was increased by (20%) to account for possible dropouts during follow-up intervals to be total of (98) cases i.e. (49) for each group. Sample size calculation was performed using G\*Power 3.1.9.2.

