### **3) Statistical methods:**

Data will be analyzed using IBM SPSS advanced statistics (Statistical Package for Social Sciences), version 25 (SPSS Inc., Chicago, IL). Categorical data will be described as absolute risk for each intervention independently and relative risk when comparing both interventions. Comparisons between categorical variables will be performed using the chi square test and Kruskal Wallis will be used to test interaction of variables. Continuous data will be described using mean and standard deviation. Comparison between continuous data will be performed using t-test and two-way ANOVA will be used to test interaction of variables. A p-value less than or equal to 0.05 will be considered statistically significant and all tests will be two tailed.

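### The protocol's only null hypothesis covers three outcomes at an unadjusted 0.05 each and ignores the protocol's own ranking, which makes salivary S. mutans count primary

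*Protocol*

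**What the plan says.** - **Hypothesis (2.2).** The single null is that the tablets "have the same effect as xylitol chewing gum on salivary pH and bacterial count in both saliva and interdental plaque". No outcome is singled out, and pH comes first in the list.
- **Research question (1.1).** It asks whether the tablets will "be better in decreasing bacterial count in both saliva and interdental plaque and elevating the salivary pH" compared with the gum. The aim (2.1) names the same three outcomes.
- **Outcome list and table (2.3, PICOTS).** The table ranks "Salivary S.mutans count" as primary; the second outcome is "interdental plaque bacterial count" and the third is salivary pH. Table 1 in the Outcomes section repeats this order.
- **Sample size calculation.** The hypothesis being powered is that the tablets "will have the better antibacterial effect than xylitol chewing gum against mutans streptococci", at alpha 0.05 and 80% power. Plaque count and pH do not enter.
- **Statistical methods.** "A p-value less than or equal to 0.05 will be considered statistically significant and all tests will be two tailed". The section does not refer to the ranking.
- **Related statements.** Outcomes are assessed at 5 minutes and at 15 days, and neither visit is named as decisive. Trial design gives the framework as equivalence.

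**The concern.** The ranking and the powering point to one outcome. The null hypothesis points to three. A null of equal effect on several outcomes is false as soon as one of them differs, and the testing rule gives each outcome its own full 0.05. An analyst who follows the Hypothesis section literally could report the trial's null as rejected because pH differed by chance, although the primary outcome showed nothing. An analyst who follows the ranking would report from the same data that the null was not rejected. The protocol does not say which is intended. What is at stake is the false-positive rate of the headline conclusion and the freedom to choose its basis after the data are seen.

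**Working it through.** **Inputs.** From the protocol: three outcomes in one null (2.2); each test two-sided at 0.05 (Statistical methods); one outcome ranked primary (2.3, Table 1); alpha 0.05 and 80% power for the mutans count (Sample size calculation); two post-baseline visits (Outcome data collection). Assumed: the correlation between the three test statistics, which the protocol does not give. It is shown as a range.

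**Step 1: the plan's own figure.** The protocol states no overall error rate. Its only figure tied to alpha is the sample size. For a chi-square test with 2 degrees of freedom, alpha 0.05 and power 0.80, w = 0.578 gives n = 29 and w = 0.43 gives n = 53. Their sum is 29 + 53 = 82, and 82 × 1.2 = 98.4, stated as 98. The figure reproduces with the full 0.05 spent on the mutans count and nothing reserved for plaque count or pH. Whether that calculation suits a comparison between arms is a separate question, not examined here.

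**Step 2: literal reading, any one of three at a single visit.** Suppose there is no true difference on any outcome.

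- Independent tests: 1 − 0.95³ = 1 − 0.857375 = 0.1426, or 14.3%.
- Upper bound under any dependence: 3 × 0.05 = 15%.
- Equally correlated normal test statistics, each rejected when |Z| > 1.96:

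| Correlation (assumed) | P(at least one significant) |
|---|---|
| 0 | 14.3% |
| 0.3 | 13.6% |
| 0.5 | 12.5% |
| 0.8 | 9.8% |

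This is 9.8/5 = 2.0 to 14.3/5 = 2.9 times the stated 5%. The independence value and the bound depend only on each test having level 0.05. The correlated values approximate the planned tests by normal statistics.

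**Step 3: reading through the ranking.** One test of salivary S. mutans count at one visit has a false-positive rate of 5%. The conclusion is then defined whatever plaque count and pH show.

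**Step 4: all three required.** The error rate is at most 5%, since every test must reject. With independent tests and no true difference anywhere it is 0.05³ = 0.0125%. This reading causes no inflation.

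**Step 5: the visit matters too.** If the literal rule ran over both post-baseline visits, six independent tests would give 1 − 0.95⁶ = 0.265, or 26.5%. Resting the null on one outcome therefore secures 5% only if one visit is also named.

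**The case against.** The strongest reply is that the hierarchy already exists. A primary outcome is named twice and is the only one powered. By convention it carries the conclusion, and the labels on plaque count and pH already mark them as lower. Read that way, the error rate is 5% for one test. Detailed handling of secondary outcomes is also commonly left to a statistical analysis plan, which is not shown.

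Much of this stands, and it rules out several stronger readings that a reader might infer:

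- **That the trial has a 14% false-positive rate, or that 14% is a ceiling.** The figure needs an any-one-outcome rule, independence and a single visit. The protocol states none of these as its rule. The bound for three tests is 15%, and two visits could push the rate higher.
- **That the conclusion is undefined when outcomes disagree.** Under the ranking it is defined.
- **That the research question and the null prescribe opposite decisions.** Neither states a decision rule. In the research question the word for both refers to the two sampling sites. Rejecting equal effect on all three is compatible with not showing superiority on all three.
- **That requiring all three outcomes would cut power to a particular value.** Any such figure needs a power for plaque count and for pH, and the protocol gives neither.

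What does not stand is leaving the matter to the analysis plan. The null hypothesis, the aim and the significance rule are fixed in the protocol. They are worded in a way that conflicts with the protocol's own ranking.

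**Conclusion.** The point holds as a conflict between the null hypothesis and the outcome ranking. Taken literally, the null is rejected by any one significant outcome, with a false-positive chance of about 10% to 14% at a single visit (correlation 0.8 to 0, assumed; bound 15%). Read through the ranking, it is 5% for one test at one visit. The first figure describes what the wording permits, not what the sponsor necessarily intends. Because a primary outcome is named and is the only one powered, this is a matter of alignment that should be settled before analysis. It does not show that the design is invalid.

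**What to change.** 1. **Hypothesis (2.2).** Restate the null, and the trial's conclusion, for salivary S. mutans count at one named post-baseline visit, tested at two-sided 0.05. The visit needs a deliberate choice: assessments are at 5 minutes and 15 days, while the sample size hypothesis refers to 1 month.
2. **Statistical methods.** State that plaque count and salivary pH are secondary, reported with 95% confidence intervals and no confirmatory claim. An acceptable alternative is to test them in the ranked order, each at 0.05, only after a significant primary result (and pH only after plaque count).
3. **Research question (1.1) and aim (2.1).** Reword to match.
4. **Trial design.** Reconcile the equivalence framework with this difference test. A non-significant difference does not show equivalence, and the protocol states no equivalence margin.

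Items 1 to 3 cost wording only, with no extra patients or measurements. Item 4 is also wording if the difference test is kept; choosing equivalence would need a margin and a new sample size. The downside is that a plaque or pH result alone could no longer be claimed as rejecting the trial's null.
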